Although there are various expert consensus' in the diagnosis of left bundle capture, the capture diagnostics has yet to be validated. In view of the limitations of left bundle capture confirmation, it remains difficult to establish confidently if there is left conduction system capture rather than left ventricular septal capture only. Furthermore, it is unclear if there is a clinically relevant advantage to left conduction system capture to left ventricular septum capture. This requires further investigation.

The paced activation patterns of the left ventricle during the lead deployment will be collected; at the left ventricular septal area (defined as more than half way beyond the septum) and the left bundle. At these points the electrical data from the pacing lead will be collected. The distal and proximal left bundle will be paced and restoration of physiological left ventricular activation will be assessed.

Challenge B: Reduced battery longevity due to high thresholds as result of limited conduction system capture discrimination by the device.

In conventional pacing, it is easy to describe to the device how to detect adequate capture, and therefore easy to have the device monitor adequacy of capture and adjust output to strike an efficient balance between ensuring capture and minimising energy consumption(9) (**Figure 1**). In conduction system pacing, we do not know how to check conduction system capture reliably using purely device-based information. Therefore, we cannot safely set the output to optimise battery life; instead, outputs are set unnecessarily high to ensure continued conduction system capture.

Checking correct capture is more difficult for conduction system pacing than conventional. It is not enough to detect capture: the device must confidently distinguish between several possible response patterns. Each patient may exhibit several patterns at different outputs. Misinterpreting the type of capture can cause harm. For example, in heart failure, if myocardium-only capture is mistakenly accepted as left bundle recruitment, patients would receive harmful right ventricular pacing rather than beneficial resynchronisation.

My aim is to develop an algorithm that can use the lead signals to reliably detect capture and classify the type of capture. I will augment the conventional lead signals with a 2 lead surface ECG from within the generator pocket. This may provide crucial additional information on type of capture.

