1.2 Original Hypothesis

Hypothesis A: A conduction system pacing protocol can be devised for use in any cath lab. **Hypothesis B:** Lead data with a novel sensing vector can detect and categorise conduction system capture, which will allow automated conduction system capture discrimination on implanted devices.

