- 2. Group 2 (24 patients): These patients will undergo
 - a. Preimplant: ECG, echocardiography, ultra-high frequency ECG, MRI
 - b. Intra-implant: Right ventricular mapping, ultra-high frequency ECG, echocardiography and ECGi
- 3. Group 3 (15 patients): These patients will undergo
 - a. Preimplant: ECG, echocardiography, ultra-high frequency ECG and MRI
 - b. Intra-implant: Right ventricular mapping, ultra-high frequency ECG echocardiography and arterial access for left ventricular mapping and invasive blood pressure monitoring

2. Validation cohort

The step by step algorithms devised from the data collected from the derivation cohort to improve the conduction system lead implant will be prospectively applied on these patients and the outcomes will be assessed. This group will consist of the second fifty patients recruited (patients 51-100).

Conduction system implant follow-up recruitment

Prospective, pseudonymised electrical data from 200 patients with a chronic conduction system device in situ, that are under follow up will be collected. They will undergo the standard clinical pacing checks and manoeuvres.

The 100 prospectively recruited patients and the 200 patients with a chronic conduction system lead will undergo a consent process. The direct care team will obtain consent to share their information with the research care team. Once the patient has consented to their information being shared, a member of the research team will contact the patient and explain the details of the research study. Written consent will be gained prior to any procedures taking place.

Patients will be consented to take part in the ECGi (Derivation Cohort, Group 2), invasive bloodpressure monitoring and left ventricular mapping (Derivation cohort, Group 3) sub-studies at the time of recruitment, until recruitment target for these sub-studies are met.

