I will work with my team to develop algorithms to reduce the impact of local muscle noise. I will improve device diagnosis of conduction system capture using standard lead data, plus the 2-lead ECG. I expect this to be achievable by identifying EGM features that are highly discriminant and organising these into a systematic algorithm with a defined sensitivity and specificity for each capture type.

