1.2 Validation

Study A:

A further 50 patients will be prospectively recruited that will make up the validation cohort for Study A. These patients will undergo a conduction system pacemaker as standard clinical practice. We will prospectively apply the step-by-step algorithm derived above to implant the conduction system lead using standard equipment alone; fluoroscopy, PSA and 12-lead ECG. We will assess the success rate, conduction system capture threshold, procedure time and fluoroscopy time. Although all operators will be highly experienced device implanters, these implants will include operators who are new to conduction system lead implantation.

The outcomes will be assessed against patients undergoing conventional methods of conduction system implantation (50 patients) and right ventricular pacing (50 patients).

Study B:

I will run the device algorithm to discriminate capture on patients 51 to 100. Through this I will establish my algorithm's accuracy with the addition of the 2-lead ECG against the gold-standard of combined 12-lead ECG, EGM and pacing manoeuvre diagnoses. These are standard clinical practices. I will test whether inclusion of the pocket EGM contributes to the algorithm's accuracy.

Follow-up

Patients will be followed up 6 weeks after device implantation and again at 1 year. These follow-up appointments will include a wound check at 6 weeks and device interrogation at 6 weeks and 1 year.

Figure 5: A flow diagram demonstrating the investigations the patient will undergo during the course of the Study A

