1.4 Study Outcome Measures

Primary Outcome Measures

A1: Success rates of conduction system lead implant (novel workflow vs conventional methods)

B1: Assess accuracy of conduction system diagnosis by the device with additional information from 2-lead ECG

- A2: Procedure and fluoroscopy times of the streamlined workflow to current conventional methods *of His-bundle and Left-bundle pacing*
- A2: Procedure and fluoroscopy times of the streamlined workflow of conduction system implant to current *right ventricular pacing*
- A2: Assess capture threshold of His-bundle and Left-bundle pacing from the optimised workflow to that of conventional methods of conduction system implantation
- A2: Define left bundle area capture diagnostics and delineate differences between left ventricular septal pacing.
- B2: Improvement in device battery life with novel device algorithm applied

5 Participant Entry

- 5.1 Pre-registration Evaluations
- 5.2 Inclusion Criteria
 - 1. Patients with a ventricular pacing indication: high grade atrioventricular block and symptomatic trifasicular, bifasicular block or left bundle branch block LBBB for cardiac resynchronisation therapy
 - 2. Adults willing to take part (ages 18 100 years old)
 - 3. Able to give consent.

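### If left bundle versus left septal capture is a B1 class, B1 can show agreement with the clinical diagnosis for it, not accuracy

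*Protocol*

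**What the plan says.** Section 1.4 (Study Outcome Measures) gives primary outcome B1 as "Assess accuracy of conduction system diagnosis by the device with additional information from 2-lead ECG". Section 4.1 (Derivation, Study B) builds the algorithm from standard lead data and the 2-lead ECG, by "identifying EGM features that are highly discriminant and organising these into a systematic algorithm". Section 1.2 (Validation, Study B) runs it on patients 51 to 100 and scores it "against the gold-standard of combined 12-lead ECG, EGM and pacing manoeuvre diagnoses". Section 1.2 (Original Hypothesis) says that capture detection from lead data and a new sensing vector "will allow automated conduction system capture discrimination on implanted devices"; B1 is the test of this.

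Section 1.1 (Background, Challenge A2) takes a more cautious view of one part of that reference. It acknowledges expert consensus on diagnosing left bundle capture, but says "the capture diagnostics has yet to be validated" and that "it remains difficult to establish confidently if there is left conduction system capture rather than left ventricular septal capture only". A secondary outcome, A2, is to "Define left bundle area capture diagnostics and delineate differences between left ventricular septal pacing". The protocol does not link A2 to the B1 reference.

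Section 8 sizes B1 so that the standard error of the proportion stays under 10 percentage points.

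**The concern.** A gold standard is treated as free of error, so that every disagreement counts against the test and every agreement counts for it. The protocol gives the composite diagnosis that status in the Validation section. In the Background it says that the diagnosis is neither validated nor confident for left bundle versus left septal capture. For that distinction the two statements do not fit together.

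EGM adds a second difficulty because it appears in the algorithm and in the reference. If a misleading EGM led both to the same wrong call, the case would be scored as correct.

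At stake is what a primary outcome can conclude. The aim is a device that classifies capture unaided, and the Background warns that misreading the type of capture can cause harm. A high B1 result would show that the device reproduces what the clinic would have said. For this distinction it would not show that the device was right.

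**Working it through.** **The plan's own figure.** Section 8 uses n = p(1−p)/SE². With p = 0.5 and SE = 0.1 this is 0.25/0.01 = 25, as stated. At the planned n = 50 the SE is √(0.25/50) = 0.0707, or 7.1 points; at p = 0.8 it is √(0.16/50) = 0.0566, or 5.7 points. The arithmetic is correct. It measures sampling error in the observed proportion and contains no term for error in the reference.

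**The passages side by side.**
- Algorithm inputs (Section 4.1): standard lead data, EGM features, 2-lead ECG.
- Reference inputs (Section 1.2, Validation): 12-lead ECG, EGM, pacing manoeuvres.
- Named in both: EGM. Whether the recordings or features are the same is not stated.
- Status of the reference: gold standard in the Validation section; for left bundle versus left septal capture, unvalidated and hard to establish in the Background.
- Capture classes scored in B1: not listed. Section 4.1 refers only to each capture type.

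**Does an imperfect reference push B1 up or down?** Let A be the true accuracy, r the reference error rate, s the share of reference errors on which the algorithm is also wrong, and m the chance that two wrong calls name the same class (m = 1 with two classes). Then

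observed agreement = A − r(1−s) + r·s·m = A + r[s(1+m) − 1].

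Agreement exceeds true accuracy only if s > 1/(1+m), that is, s > 0.50 at m = 1 or s > 0.67 at m = 0.5. The protocol gives none of A, r, s or m. The values below are assumptions chosen to show the sign, with A = 0.80:

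| r | s | Agreement, m = 1 | Agreement, m = 0.5 |
|---|---|---|---|
| 0.05 | 0.4 | 0.79 | 0.78 |
| 0.05 | 0.6 | 0.81 | 0.795 |
| 0.10 | 0.4 | 0.78 | 0.76 |
| 0.10 | 0.6 | 0.82 | 0.79 |

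Agreement runs from 4 points below the assumed truth (0.76) to 2 points above it (0.82). With independent errors s = 1 − A = 0.2, and at m = 1 agreement is 0.77 (r = 0.05) or 0.74 (r = 0.10), below the truth in both cases. The sign depends on quantities the protocol does not give. The sample size does not enter the formula, so more patients would not remove the discrepancy.

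**The case against.** The strongest reply has four parts.

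- **The class is assumed.** B1 lists no capture classes. The example that motivates the algorithm in Section 1.1 (Challenge B) is myocardium-only capture mistaken for left bundle recruitment, which is a different distinction. This stands, and it is why the point is conditional. Section 1.1 also says it is unclear whether left bundle capture has a clinically relevant advantage over septal capture, which limits the weight of the point.
- **The reference is named openly and is standard practice.** Accuracy against a named clinical reference is common usage, and consensus criteria exist. This stands for the reference in general. It does not meet the protocol's own statement that the left bundle criteria are unvalidated.
- **The overlap is partial.** The reference also uses 12-lead ECG and pacing manoeuvres, and the algorithm's output is no part of it. This stands. A reader might infer that the algorithm is marked against itself and that B1 must be inflated. The document does not support that: shared use of the same EGM signals is not stated, and an imperfect reference can lower agreement as well as raise it. In the illustration the net shift is smaller than one standard error at n = 50 (5.7 points at p = 0.8).
- **The gap is already being worked on.** A2 and the left ventricular maps at deep septum and left bundle come from derivation patients, so their results could be available before B1 is scored. This stands in part, since no text carries them into B1. The remark in Section 4.1 that mapping and echocardiography will help validate the algorithm concerns the implant guide of Study A. The Study B validation text names only the composite.

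Rules for blinded reading and for indeterminate recordings may properly sit in a statistical analysis plan, and their absence is not a fault here.

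**Conclusion.** The point holds in a limited form. The reference, its description as a gold standard and the word accuracy are all fixed in the protocol, and for one distinction they conflict with the Background. If left bundle versus left septal capture is among the B1 classes, B1 as defined measures agreement with the composite clinical diagnosis for that distinction, and the Section 8 standard error does not cover error in that diagnosis.

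No size or direction of bias is claimed. Every input to the illustration is assumed, and it serves only to show that the sign is open. A reader might extend the point to B1 as a whole. The document does not support this: it does not call the reference unreliable for His-bundle or myocardium-only capture. The change is worth making because it alters what a primary outcome may conclude.

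**What to change.** 1. In Sections 1.2 (Validation), 1.4 and 8, and where the Study Summary repeats B1, replace the gold-standard and accuracy wording with agreement with the composite clinical diagnosis, at least for left bundle versus left septal capture. Limit the conclusion on Hypothesis B to match.
2. List the capture classes that B1 scores. Report left bundle versus left septal results separately, with the A2 findings from the derivation cohort stated beside them.
3. Keep the composite as the main reference. Add a sensitivity analysis in patients 51 to 100 against a reading from 12-lead ECG and pacing manoeuvres without EGM, using recordings already planned.

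**Cost.** Items 1 and 2 are wording and reporting. Item 3 needs one extra reading and no new patients or procedures. Its reference is weaker: without EGM the criteria in the Appendix table that rest on the His signal are lost, so more recordings, mainly His-bundle, will be indeterminate. The 2-lead and 12-lead ECG also remain related. A discrepancy would therefore show dependence on the EGM, not the size of any bias.

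**Optional and descriptive only.** The composite could be compared with left ventricular maps (15 patients) or ECGi (24 patients) in the derivation cohort. Both tests are optional for patients, ECGi at both lead positions is not stated, and judging agreement partly needs the criterion that A2 is meant to define. The numbers are also small. With no disagreements the one-sided 95% upper limit for reference error, 1 − 0.05^(1/n), is still 18% at n = 15 and 12% at n = 24.

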1.3 Burden/Risk

The main burdens for the patient include:

- The extra time taken to perform the experiments and experimental procedures during their scheduled clinical procedure due to the additional diagnostic investigations. The right heart electro-anatomical mapping will add 10 minutes. The echocardiography will add an additional 5 minutes. Those who consent to left ventricular maps will have an additional 14 minutes (7 minutes per map).
- 2. The extra access in the groin in those who consent to have an intracardiac echocardiography or left ventricular map (femoral vein and artery respectively).
- 3. The extra procedure of transoesophageal echocardiography in those who consent for this
- 4. Patients receiving unconventional therapy with conduction system lead implantation

The burden will be mitigated by the minimum extra time being used to complete the experiments, the use of local anaesthetic and the immediate removal of extra research related sheaths as soon as they are not needed

The main risks for the patient are:

A conduction system pacing wire is not known to have a higher complication rate compared to a conventional pacing wire. Conduction system pacing wires have been shown to be as effective as conventional pacing wires at preventing slow heart rates and improving heart pumping. If a complication occurs and the conduction system pacing wire cannot be implanted or does not perform as expected during follow-up a procedure will be performed to convert your pacing system to a conventional pacing system.

The additional risks of arterial tube placement include:

- 1% risk of bruising around the area
- 1 in 1000 risk of damage to the blood vessels requiring surgery
- Less than 1 in 500 risk of stroke
- The additional risks of transoesophageal echocardiogram include

• 1% risk of damaging the food-pipe or wind-pipe including a 1 in 1000 risk of perforating the food-pipe.

The additional risks of intracardiac echocardiogram include

- 1% risk of bruising around the access area in the leg
- Less than 1 in 1000 risk of heart perforation

The additional risks of electro-anatomical mapping include

Less than 1 in 1000 risk of heart perforation

Therefore, the overall risk of serious complications arising from taking part in the research study are less than 4 in 1000 (0.4%)

Participants in this study will have a chest CT scan which is not part of standard care. Pacemaker implantation involves exposure to ionising radiation to visualise lead implantation. Taking part in this study involves exposure to additional exposure to radiation above the standard clinical procedure due to the additional measurements that will be taken.

Ionising radiation can cause cell damage that may, after many years or decades, turn cancerous. We are all at risk of developing cancer during our lifetime. The normal risk is that this will happen to about 50% of people at some point in their life. Taking part in this study will increase the chances of this happening to you from 0.01% to 0.1%

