Figure 3: A diagram to illustrate patient recruitment for **Study A**. A total of 100 patients will be recruited. Patients 1-50 will be the derivation cohort and 51-100 will be the validation cohort. Within the derivation cohort, some patients will undergo ECGi, additional arterial access and intracardiac echo (ICE), some will undergo two of these additional tests, some will undergo one and some will not undergo any at all. All patients in the derivation cohort will undergo preimplant ECG, echocardiography, ultra-high frequency ECG (UHF ECG) and MRI, as well as right ventricular mapping, UHF ECG and echocardiography during the implant.

Figure 4: Recruitment of patients in Study B

4. Methodology

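### The bound of <4 serious complications per 1000 does not follow from the protocol's own list for arterial access with ICE or TOE, and its chest-CT and cancer-risk sentences need reconciling

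*Protocol*

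**What the plan says.** The Burden/Risk section of the protocol gives added risks procedure by procedure.

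- **Arterial access:** "1 in 1000 risk of damage to the blood vessels requiring surgery" and "Less than 1 in 500 risk of stroke", besides a 1% risk of bruising.
- **TOE:** "1% risk of damaging the food-pipe or wind-pipe including a 1 in 1000 risk of perforating the food-pipe".
- **ICE:** "Less than 1 in 1000 risk of heart perforation", besides a 1% risk of bruising.
- **Mapping:** under the line "The additional risks of electro-anatomical mapping include" there is a single item, the same perforation limit as for ICE.

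It then draws one conclusion from these items, introduced by the word therefore: "the overall risk of serious complications arising from taking part in the research study are less than 4 in 1000 (0.4" per cent). It names no pathway and no averaging rule.

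The caption of Figure 3 (Section 3, Recruitment) says that, within the derivation cohort, "some patients will undergo ECGi, additional arterial access and intracardiac echo (ICE"), while others have two, one or none of these tests. It adds that every derivation patient has the pre-implant tests "as well as right ventricular mapping, UHF ECG and echocardiography during the implant". Section 3 (Group 3) and Section 4.1 put the arterial-access group, which also has left ventricular mapping, at 15 of 50. The echocardiogram item of Section 4.1 gives patients without ICE either transthoracic echo, if the windows are adequate, or TOE.

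On radiation, the Burden/Risk section says without restriction that participants will have a chest CT outside standard care. The ECGi item of Section 4.1 places the CT within ECGi, for a subgroup, and calls the procedure optional. Section 3 sets that subgroup (Group 2) at 24 patients. The Burden/Risk section also gives a normal lifetime cancer risk of about 50% and then says that taking part raises the chance from 0.01% to 0.1%.

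**The concern.** The overall figure is presented as a consequence of the list above it, so it should follow from that list for every patient to whom it applies. If the bound is already exhausted by one set of procedures, it cannot also cover patients who have a further invasive procedure on top. Those are the patients for whom a summary risk figure matters most.

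The CT sentence raises a question of scope: it attributes an added exposure to all participants when the methods describe it for an optional subgroup. The cancer-risk sentence cannot be read literally beside its own baseline.

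These are the protocol's stated safety and exposure figures. What is at stake is their accuracy. The statistical design is not touched.

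**Working it through.** **Inputs (per 1000, Burden/Risk section).** Vessel damage needing surgery 1; stroke <2 (1 in 500); mapping perforation <1; ICE perforation <1; TOE perforation 1. Bruising is left out as not serious. For TOE only perforation is counted, because the section does not say whether the rest of the 1% injury risk is serious. ICE and TOE are alternatives in Section 4.1, so they are never added together. The mapping limit is counted once, as listed.

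**Formula.** Bound for a pathway = sum of the limits of its components.

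**Step 1: reproduce the stated figure.** Arterial access + mapping + transthoracic echo: 1 + <2 + <1 = <4. This matches the protocol.

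**Step 2: add the invasive echo options.**

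| Pathway | Sum of limits per 1000 | Stated |
|---|---|---|
| Arterial + mapping + transthoracic echo | 1 + <2 + <1 = <4 | <4 |
| Arterial + mapping + ICE | 1 + <2 + <1 + <1 = <5 | <4 |
| Arterial + mapping + TOE | 1 + <2 + <1 + 1 = <5 | <4 |

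**Step 3: does simple addition matter?** Treating the events as independent, at their limits:

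- 1 − (0.999 × 0.998 × 0.999) = 3.995 per 1000 for the first row;
- 1 − (0.999 × 0.998 × 0.999 × 0.999) = 4.991 per 1000 for the other two.

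The conclusion is the same.

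**Step 4: who is affected.** Arterial access is planned for 15 of 50 derivation patients, which is 15 of 300 overall (5%). How many of the 15 will have ICE or TOE is not stated, so 15 is a ceiling.

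**Step 5: the figure as an average over the derivation cohort.** All 50 have mapping (<1) and 15 have arterial access (<3).

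- All with transthoracic echo: (50×1 + 15×3)/50 = <1.9 per 1000.
- All with ICE or TOE: (50×1 + 15×3 + 50×1)/50 = <2.9 per 1000.

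Either way <4 would hold.

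**Step 6: CT.** The ECGi group is 24/50 = 48% of the derivation cohort and 24/300 = 8% of all participants. The validation implants in Study A use standard equipment alone, and the 200 follow-up patients attend routine checks with a 2-lead ECG added; neither description includes a CT.

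**Step 7: cancer risk.** A chance whose normal value is about 50% cannot start at 0.01%. The sentence makes sense only if the two percentages are something else, such as a range for an added absolute risk. That reading is an assumption.

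**The case against.** The strongest defence is that the figure is reproducible and contradicts nothing. It equals the sum for arterial access plus mapping with transthoracic echo, the first option named for patients without ICE. Stroke, mapping and ICE carry less-than limits, so a true total below 4 per 1000 is compatible with every listed item even when ICE or TOE is added. The wording speaks of overall risk from taking part, which could mean an average, and on that reading the bound holds. On radiation, Section 4.1 is clear about who is scanned, and the cancer-risk sentence looks like a slip of wording.

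Much of this stands. It limits the point to a bound that is not derived for some planned patients. It does not remove the point: limits that sum to <5 do not yield a bound of <4, and the text says neither that the figure is an average nor that it excludes the combined pathway.

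Three stronger readings are tempting, and the documents support none of them.

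- *The true risk exceeds 4 per 1000.* The components are mostly upper limits, so this cannot be inferred.
- *The right total is <6.* This requires counting the mapping limit once for each ventricle. Section 4.1 treats electro-anatomical mapping as one procedure with right and left parts, and the Burden/Risk section gives it one limit. Doubling it is an assumption.
- *The whole 1% TOE injury risk belongs in the total.* The section does not classify the non-perforating part as serious.

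**Conclusion.** The point holds as a minor error in the protocol's text. The listed serious items support <4 per 1000 for arterial access plus mapping with transthoracic echo, and <5 per 1000 once ICE or TOE is added. The second case is permitted by Sections 3 and 4.1 and concerns at most 15 of 50 derivation patients. This rests on excluding bruising, counting only perforation for TOE, counting the mapping limit once, and taking the lists as they stand. The lists are introduced as what the risks include, so the sums cover listed items only.

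The unrestricted chest-CT sentence conflicts with the ECGi item of Section 4.1. The cancer-risk sentence does not fit the baseline given just before it; that clash lies within the Burden/Risk section itself.

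**What to change.** **Overall bound (Burden/Risk section).** Do one of two things:

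- restate it for the pathway with most added procedures as <5 per 1000 (0.5%) from the listed items, saying whether the single mapping limit covers both ventricles and whether non-perforating TOE injury counts as serious; or
- state that the figure is an average over a named cohort, and give its basis.

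**Radiation paragraphs (same section).** Limit the CT sentence to the optional ECGi subgroup. Reconcile the cancer-risk sentence with the 50% baseline, for example as an added absolute risk of 0.01% to 0.1% if that is what is meant. Check any other study document that repeats these figures.

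**Cost.** A short text amendment. If the figure is kept as a per-patient bound, it becomes slightly less favourable. Procedures, endpoints, sample size and analysis stay as they are.
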